### **Study Objectives:**

To examine physician- and patient-based interventions designed to decrease overscreening and overtreatment by increasing adherence to US guidelines for women under 30 years of age. Specifically, the interventions will focus on increasing average intervals between screening and decreasing the number of colposcopy examinations and excisional procedures. The long-term objective is to identify effective strategies to increase adherence to screening guidelines nationwide.

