## **STUDY METHODOLOGY**

### **Study Intervention**

#### *Choice of Comparators*

We will compare 2 different interventions arms that are designed to prevent overscreening and over treatment by increasing adherence to the new US cervical cancer screening guidelines and the ASCCP guidelines for the management of abnormal cervical cancer screening tests and cancer precursors. Specifically, the interventions will focus on lengthening cervical cancer screening intervals to every 3 years, decreasing colposcopy procedures for minimally abnormal cytology results and decreasing treatment of cervical precancerous lesions with a high rate of regression (i.e., cervical intraepithelial neoplasia grades 2 and 2/3).

The two arms will be:

- 1) Mobile application (APP)-based intervention for providers,
- 2) Mobile application (APP)-based intervention for providers PLUS patient-centered approach intervention (PCA).

The two arms will be compared to a comparison group (no intervention).

The APP-based intervention (APP) is for clinicians' mobile phones and will maneuver them through current guidelines (cervical cancer screening and management of abnormal cytology and histology) based on patient age and condition. This is the current ASCCP tool, which will be updated to include screening guidelines and risk assessment so the provider can better understand the risk associated with follow-up versus premature triage to colposcopy.

The patient-centered approach intervention (PCA) is oriented towards educating women about HPV and cervical cancer screening. The intervention will be provided to patients' when they check-in for a clinic appointment, and will interactively provide information designed to help them understand current guidelines for the frequency of cervical cancer screening and appropriate management for abnormal cytology and treatment options. It will allow them to assess the risks and benefits of screening intervals and of treatment choices.

Comparison sites will have no intervention.

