### **Sample Size Estimates and Power Calculations**

The database for FY 2010/11 shows that 386 clinics fit the criteria with 89 sites available for arms 1-2 and 297 available for the comparison group. The mean number of female clients aged 21-29 years seen at the eligible clinics was 560 and the mean number of cytology specimens, colposcopic examinations and LEEP/cryoprocures for this age group was 297, 40, and 4, respectively. In 2012, the mean cytology interval was 19 months. Very few clinics had an interval >30 months. There were no differences for any of the above variables between those

sites eligible for intervention and those for comparison. These numbers have not changed significantly in the past 2 years and will be updated for the baseline assessment.

After enrolling 7 sites into each arm, we estimate that we would have approximately 2800-3500 women aged 21-29 years in each arm. For each arm, baseline cytology rate in this age group would be approximately 50%, rate of colposcopy procedures for those who had cytology would be 13%, and rate of LEEP/cryotherapy procedures for those referred to colposcopy would be 10%.

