Sample size calculations for the primary endpoint (rate of cytology testing) are based on a pairwise comparison of observed changes from baseline in clinic-specific three-month testing rates between intervention study arms (APP or APP+PCA) and the control arm, using a t-test adjusted for clustering on the clinic level. The baseline rate in control clinics is assumed to be approximately 50%, consistent with the preliminary data presented above. Assuming that there will be no observed change in rates for control clinics during the testing period, our expected sample size of 9030 (i.e. 3010 per arm, seven clinics per arm, and an average of 430 women per clinic) will be sufficient to provide 90% power to detect a between-arm difference as small as 16% as significant. This calculation assumes a quite conservative value for the intracluster correlation of outcomes within clinics of 0.07, and is based on a 1% significance level to account for the fact that there will be two pairwise comparisons with the control arm (i.e. one per intervention arm). Accounting for as much as 10% missing data on testing rates, we will still retain more than 90% power to detect differences of this magnitude or larger between arms as significant at the 5% level. We should also retain adequate power to conduct additional sensitivity analyses investigating the possible confounding influence of clinic-level descriptors (e.g. race/ethnicity and age distribution) on observed results. Finally, we note that our proposed analysis that will account for within-clinic paired observation of outcome rates and adjust for baseline covariates will likely yield more power than the conservative estimates made above. Although the study is not powered to detect significant differences between intervention groups, a similar calculation for the comparison between the APP and APP+PCA groups indicates that we retain at least 70% power to detect a difference in observed changes in testing rates as small as 15% as significant at the 5% level.

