Parallel calculations for the secondary colposcopy outcome also are based on between-arm comparison of changes in three-month colposcopy rates from baseline levels, and assume that approximately 50% of women will receive cytology at baseline and follow-up in the control group, and that colposcopy rates will also remain unchanged at 13%. We also assume that the intervention-related reduction in cytology will result in approximately 20% fewer women eligible for colposcopy at follow-up. Based on similar assumptions about intracluster correlation and loss to follow-up, results indicate that with the planned total sample size of 9030, we will retain at least 80% power to detect an intervention-related reduction in colposcopy rate as small as 8% at the 5% (one-sided) significance level. Due to our conservative assumptions, we should have sufficient power to detect even smaller intervention-related effects in analyses adjusting for baseline characteristics.

We did not perform calculations for the testing interval length and LEEP outcomes because of the lack of preliminary data on their potential variability within and between clinics.

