**b) To increase average length of cervical cytology testing among women under 30 years of age**

**Pre:** cervical cytology test interval among women who received two CC tests from same provider (analysis limited to providers who have been in program at least 36 months)

**Post:** cervical cytology test interval among women who received their second CC test 3-15 months after the intervention started.

**c)** To decrease the number of LEEP and cryotherapy procedures in women under 30 years of age with abnormal cytology.

**Pre:** Rate of women 21-29 years of age who receive LEEP or cryotherapy over total number of women 21-29 years of age in quarter before intervention started.

**Post:** Rate of women 21-29 years of age who receive colposcopy or LEEP or cryotherapy over total number of women 21-29 years of age in 3-6, 9-12, and 15-18 months after intervention started.

**d)** To decrease the number of colposcopy procedures in women 21-24 years of age with abnormal cytology.

**Pre:** Rate of women 21-24 years of age who receive colposcopy over total number of women 21-24 years in quarter before intervention started.

**Post:** Rate of women 21-24 years who receive colposcopy over total number of women 21-24 years of age in 3-6, 9-12, and 15-18 months after intervention started.

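### The secondary interval endpoint counts only women re-tested in months 3-15 and does not censor the rest, so long deferral can be understated and a longer delay can read as a smaller rise

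*Combined protocol and SAP*

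**What the plan says.** Longer screening intervals are a named aim. Study Objectives states that "the interventions will focus on increasing average intervals between screening", and Choice of Comparators describes "lengthening cervical cancer screening intervals to every 3 years". The starting point is given under Sample Size Estimates and Power Calculations: "In 2012, the mean cytology interval was 19 months".

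Item b) of Data Analyses is the only endpoint expressed as an interval. Its pre value is the "cervical cytology test interval among women who received two CC tests from same provider", restricted to providers with at least 36 months in the program; no date window is given for the second test. Its post value is the "cervical cytology test interval among women who received their second CC test 3-15 months after the intervention started". The text that follows the outcome list makes it a secondary endpoint, limits it again to women with two tests from one provider, and analyses it like the primary, by a clustered t-test on within-clinic change.

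Missing Data and the section on sensitivity and heterogeneity cover late claims, incomplete records and a leave-one-clinic-out jack-knife. Neither mentions censoring, a time-to-event method, or women not re-tested by month 15. No power calculation was made for this endpoint, because of the "lack of preliminary data on their potential variability within and between clinics".

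**The concern.** A woman is counted after the intervention only if her next test happens inside a 12-month window. An intervention that works moves tests later, and tests moved past month 15 leave the average altogether. From a mean of 19 months to a target of 36, the average woman would have to defer by 36 - 19 = 17 months, which is longer than the window can show. Women who follow the guideline most closely are therefore among the most likely to be excluded. A deferred test is not missing data, so the missing-data provisions do not reach it.

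Two consequences follow. The endpoint can report a rise well below the true one. The measured rise also need not grow with the true one, so two arms could appear in the wrong order. That bears on the hypothesis under Choice of Outcomes that the combined intervention does better than the provider intervention alone, although the plan says "the study is not powered to detect significant differences between intervention groups".

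**Working it through.** The plan gives no effect size, spread or power for this endpoint, so there is no figure to reproduce. The check asks what item b) would measure for a known true change.

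**Inputs from the plan.** Window: months 3 to 15 (Data Analyses, b). Baseline mean: 19 months (Sample Size Estimates and Power Calculations). Target: 36 months (Choice of Comparators).

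**Assumptions.** The share p of women who defer, the delay D, and the shape of the interval distribution. None is in the documents.

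**Closed form.** Let due dates be spread evenly over time, and from month 0 let a share p defer their next test by D months, with D between 3 and 15. Women who do not defer fill all 12 months of the window. Deferred tests appear only from month D to month 15.

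- Deferrers' share of counted tests = p(15 - D) / [12(1 - p) + p(15 - D)]
- Measured rise = D × that share
- True rise = pD

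For p = 0.5:

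- D = 6: 6 × 4.5/(6 + 4.5) = 2.57, true 3.0
- D = 9: 9 × 3/(6 + 3) = 3.00, true 4.5
- D = 12: 12 × 1.5/(6 + 1.5) = 2.40, true 6.0
- D = 17: no deferred test falls in the window, so the measured rise is 0, true 8.5

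For p = 0.25, the measured rises at D = 6, 9, 12 and 17 are 1.20, 1.29, 0.92 and 0, against true rises of 1.50, 2.25, 3.00 and 4.25. In both series the measured rise climbs and then falls while the true rise keeps growing.

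**Renewal simulation.** Gamma intervals, mean 19 months, shapes 2, 4 and 8 (SD = 19/√shape, about 13.4, 9.5 and 6.7 months). A changer's next test either moves to at least a fixed number of months after her last test (*wait*) or is postponed by a fixed amount (*delay*). With no effect the window mean is 19.0. Ranges run over the three shapes.

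| Change in behaviour | True rise (months) | Measured rise (months) | Captured |
|---|---|---|---|
| One third wait at least 36 months | 5.6-6.0 | 1.1-2.3 | 20-38% |
| Half wait at least 36 months | 8.5-9.1 | 2.2-4.2 | 25-46% |
| Half delay 12 months | 6.0 | 2.4-2.5 | 39-41% |
| Half wait at least 30 months | – | – | 56-68% |
| Half wait at least 24 months | – | – | 87-95% |
| Half delay 6 months | 3.0 | 2.6-3.0 | 86-101% |
| All wait 36 months | – | – | 102-122% |
| All delay 3 months | 3.0 | 3.2-4.1 | 107-136% |

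**Order, at shapes 2 / 4 / 8.**

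- Half delaying 12 months: 2.46 / 2.44 / 2.44. Half delaying 6 months: 3.04 / 2.75 / 2.62. Reversed at every shape.
- One third waiting 36 months: 2.31 / 1.68 / 1.18. One third waiting 24 months (true rise only 2.0-2.8): 2.42 / 1.94 / 1.67. Reversed at every shape.
- Half waiting 36 months: 4.21 / 3.10 / 2.22. Half waiting 24 months: 4.00 / 3.18 / 2.66. Not reversed at shape 2, nearly tied at shape 4, reversed at shape 8.

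**Other distributions.** With gamma (SD 5 and 8), lognormal (SD 10) and a 12/26-month mixture, half moving to 36 months gives a measured rise of 1.5-3.0 against a true 8.0-8.3. The closed form shows no bias for delays of 3 months or less, so the overstatement in the last row of the table comes from the simulation only and depends on shape.

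**The case against.** The strongest reply is that nothing spurious arises. All groups share the window, so without an effect there is no between-arm bias; in the understated scenarios a real effect is attenuated, on one secondary endpoint with no claimed power. This is correct, and it limits the severity.

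The primary rate also keeps women who were not tested in its denominator and runs to month 18. If half of women wait to 36 months, tests in the window fall by 38-43%. With visits unchanged (an assumption) and the plan's 50% baseline, that is 0.38 × 50 = 19 to 0.43 × 50 = 21.5 points, above the 16% difference the study is sized for. If one third wait, the fall is about 13-14 points, below it. So the primary covers much of the worst case, but it does not say how long intervals became.

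The arm-order risk is modest. Most modelled reversals are 0.1 to 0.6 month, and they need arms that differ in length of delay rather than in uptake. If the combined arm only raises uptake of a 36-month wait, the order holds (1.1-2.3 for one third, 2.2-4.2 for half). The reversal is a possibility, not a forecast.

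The 19-month figure may itself be a mean of intervals completed within three years, since the Inclusion Criteria calculate it from the last 3 years. The underlying mean would then be about 19.4 months at shape 8, 21.5 at shape 4 and above 30 at shape 2. That alters magnitudes, not the direction of the argument.

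A lighter remedy would report the share not re-tested by month 15 beside the mean. That discloses the problem, but the tested quantity could still fall as the delay grows.

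**Conclusion.** The concern holds. Item b) selects women on the event under study, and no other section corrects for it. The measured rise is understated when a minority or about half of women defer for long (about 30 months or more between tests, or 12 extra months). It is mostly captured when half wait only to 24 months or delay by 6, and overstated for a uniform 3-month delay or if all wait 36 months. It can also fall as the true effect grows.

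The sizes are illustrative and rest on the assumed uptake, delay and interval distribution. The selection itself, and the possibility of reversal, follow from the window. The harm is confined to this secondary endpoint; the primary testing rate is not affected by the selection. The change should be made because longer intervals are a stated aim, no other endpoint measures them as intervals, and the correction is cheap.

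**What to change.** For every woman with a prior cytology at the clinic, analyse time from last to next cytology:

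- Delayed entry at month 3, or at her last test if later.
- Administrative censoring at month 15, or at the end of available claims for all women, never at her own last claim.
- The same 12-month window and look-back in the pre period. To reach 33 months by month 15, the look-back must include last tests at least 33 - 15 = 18 months before the start.
- Compare clinic-level changes in the Kaplan-Meier proportion re-tested by 24 and by 33 months with the planned clustered t-test.
- Keep the mean among re-tested women as descriptive, and state how women who turn 30 while waiting are handled.

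In the same simulations the proportions re-tested by 24 / 33 months are:

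| Scenario | By 24 months | By 33 months |
|---|---|---|
| No effect | 0.72-0.79 | 0.86-0.97 |
| Half delay 6 months | 0.61-0.62 | 0.79-0.90 |
| Half delay 12 months | 0.45-0.51 | 0.66-0.70 |
| Half wait 24 months | 0.42-0.43 | 0.81-0.96 |
| Half wait 36 months | 0.43-0.45 | 0.56-0.59 |

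Both time points are needed: waits of 24 and 36 months look alike at 24 and separate at 33.

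Precision looks workable. The plan reports that "the mean number of cytology specimens, colposcopic examinations and LEEP/cryoprocures for this age group was 297, 40, and 4" respectively, for a mean of 560 women per clinic. Taking women as independent, the clinic-level sampling SD of the 24-month proportion is 0.02-0.03 at 297 tests a year, and 0.04-0.06 in a 200-woman clinic (200 × 297/560 = 106 tests).

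The cost is SAP wording and programming. The plan warns of limited patient-level data, but this needs only the per-woman test dates that item b) already requires. The headline becomes a proportion rather than months, and overlaps in part with the primary rate. Women who leave the clinic count as not re-tested there, which should be stated as a limitation. If 26% left after each test (an assumption borrowed from the 74% four-year retention under Study Population), the 24-month fall when half wait 36 months would shrink from 0.27-0.36 to 0.22-0.27. The 12- and 6-month delays would stay in the right order (0.33-0.35 against 0.44-0.45).

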## **PROJECT SUMMARY**

**BACKGROUND** Screening with cytology has accompanied large decreases in cervical cancer mortality in the US. However, cytology remains a relatively non-specific test resulting in needless invasive procedures for many women. Studies show that young women are specifically vulnerable since over-screening results in overtreatment with excisional therapies that have been associated with premature delivery and emotional distress. Current national guidelines recommend that routine screening be performed at less-frequent intervals and excisional cervical therapies are discouraged in young women. Uptake of these guidelines has been low for several reasons: many women expect annual cytology, physicians may have financial incentives and/or are not aware of current guidelines. **OBJECTIVES** To examine physician- and patient-based interventions designed to decrease overscreening and overtreatment by increasing adherence to US guidelines for women under 30 years of age. Specifically, the interventions will focus on increasing average intervals between screening and decreasing the number of excisional procedures. The long-term objective is to identify effective strategies to increase adherence to screening guidelines nationwide. **METHODS** We will conduct a randomized intervention clinic with two arms and use Family PACT administrative data for sampling, baseline, and outcome assessment. We will select 14 clinics from the Family PACT provider network that evaluate at least 200 female clients under 30 years of age per year. Clinics will be randomized to 1 of 2 arms: 1) mobile application (APP)-based intervention for providers, and 2) APP-based intervention for providers plus patient-centered approach (PCA) intervention. These groups will be compared to a comparison group of 7 clinics chosen at random (those not randomized). The APP intervention is for clinicians' mobile phones and will maneuver them through current guidelines based on age and condition. The PCA intervention will be patients' education using a tablet at the time of check-in to assist in understanding guidelines, asking questions of their providers, and assist them in evaluating treatment options. Family PACT serves predominantly uninsured women and 40% of clients are Latina. Development of the interventions will be conducted with input from all stakeholders including women from the community who are members of the National Cervical Cancer Coalition, and the Latina Contra Cancer, the American Congress of Obstetricians and Gynecologists, the State Office of Family Planning, the American Society for Colposcopy and Cervical Pathology and Quest laboratories. We plan to enroll 7 sites into each intervention arm with an average of 2800 to 3500 women aged 21-29 years per arm with a similar number of sites and women randomly chosen for the comparison arm resulting in a total of 21 sites and 8400-10500 women. Outcomes will be compared between study arms using t-test adjusting for clustering by clinic. **PATIENT OUTCOMES** We will use Family PACT claims data to calculate for each clinic by age, the number of and average interval between cytology specimens, colposcopy examinations and the number of excisional procedures. **SIGNIFICANCE** We will define successful interventions that will reduce unnecessary screening and treatment for cervical cancer screening in young women.

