Using ASCUS or LSIL as a cut off results in referring thousands of women who do not need colposcopy and biopsy whereas using HSIL as a cut off results in missing significant disease including cancer. Biopsy is also not without risk in that infection or bleeding, although rare, can occur. Treatments for abnormal biopsy results include ablative (i.e. cryotherapy (freezing), electric dissection, cold coagulation and laser ablation) and excisional (i.e. Loop electrosurgical excision therapy (LEEP), laser conization and cold-knife conization). None of these procedures are without risk. All can be associated with pain, bleeding and infection as well as psychological distress, anxiety and fear. LEEP has become the modality of choice for most practitioners. Cryotherapy has lost appeal since treatment with cryotherapy of large lesions can result in recurrences and excisional therapies allow the margins of the lesions to be evaluated by a pathologist. Although controversial, margins with evidence of disease are more commonly associated with recurrences. There have been a few meta-analysis and systematic reviews examining birth outcomes after CIN treatment. Crane et al in systematic review found that women who had LEEP were more likely to have preterm birth (OR =1.81 95% Confidence Interval (CI) 1.18, 2.76) and low birth weight infants (<2500 g) (OR=1.60, 95% CI 1.01, 2.52; P = .04). No differences were found in C-section, labor induction or neonatal intensive care unit admission. The finding for preterm birth persisted even when controlling for smoking status. In a prospective study, Crane and colleagues reported that LEEP and cold knife procedures were both associated with preterm birth. Two small meta-analysis found that excisional but not ablative treatment was associated with preterm birth. A recent meta-analysis of excisional and ablative therapies by Bruinsma and Quinn found that preterm birth was increased in women who received excisional therapy compared to both a population based (OR=1.97 95% CI 1.78-2.17) and hospital based (OR=2.71 95% CI 1.89-2.49) comparator. Ablative treatment was also associated with increased risk compared to population-based comparators (OR=1.53 95% CI 1.32-1.78) but not Hospital- based. This meta-analysis also compared treatment to women with CIN but no treatment. In this comparison, excisional (OR=1.25 95% CI .98-1.58) had a smaller affect and ablative was not significant (OR = 1.03 95% CI 0.9-1.18).

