### *Development of the PCA Intervention*

Four focus groups will be held both English and Spanish speaking, separately. With the assistance of NCCC and LCC, our patient stakeholders women aged 21-29 years of age will be identified for each focus group (See **Appendices A & B** for Focus Group Scripts). The focus groups will review the guidelines and their rationale and ask women what messages would be most appropriate and acceptable to the target population. Women with cancer, CIN and no abnormal cervical cytology will be targeted for inclusion whenever possible. Women who have never been screened for cervical cancer also will also be sought to participate. Issues that will be addressed include fears, concerns, and areas of uncertainty she may have around screening, and potential messages that could be used to address these issues. Thematic areas will focus on: cervical cancer screening intervals in young women under 30 years; natural history of HPV, follow-up of ASCUS and LSIL cytology by cytology only in women aged 21-24 years vs. immediate referral to colposcopy, follow-up of biopsy proven LSIL by cytology without treatment, follow-up of biopsy proven HSIL by colposcopy and cytology vs. immediate treatment, treatment options (cryotherapy vs. excisional therapy).

Transcriptions of the oral discussions of the focus groups will be taken and distributed to the group. Based on the transcriptions, we will develop a paper tool.

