## ANALYTIC METHODS

### Research Question

Does provision of patient and provider educational materials increase adherence to cervical cancer screening guidelines (increase in screening interval and decrease in diagnostic and excisional procedures) in women under age 30?

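### Outcome (c) counts LEEP and cryotherapy together and names no conization, so it cannot isolate the change in excisional procedures that the objectives ask about

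*Combined protocol and SAP*

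**What the plan says.** Three places set the target as excisional procedures:

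- Study Objectives: "increasing average intervals between screening and decreasing the number of colposcopy examinations and excisional procedures".
- Research Question (Analytic Methods): "increase in screening interval and decrease in diagnostic and excisional procedures".
- Project Summary, listing what will be calculated from claims: "the number of and average interval between cytology specimens, colposcopy examinations and the number of excisional procedures".

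The Background (Impact of Condition on Health of Individuals and Populations) gives the plan's own classification. Cryotherapy heads the ablative list. The other list is "excisional (i.e. Loop electrosurgical excision therapy (LEEP), laser conization and cold-knife conization".

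Under Data Analyses, aim (c) is "To decrease the number of LEEP and cryotherapy procedures in women under 30 years of age with abnormal cytology". Its Pre numerator is women with LEEP or cryotherapy. Its Post numerator is women with colposcopy, LEEP or cryotherapy. The paragraph on secondary endpoints again takes LEEP and cryotherapy as one item. Conization appears in none of these definitions, and Choice of Outcomes speaks only of cervical procedures in general. The excisional count promised in the Project Summary is not defined anywhere in the Analytic Methods.

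**The concern.** A secondary outcome should answer the question it is attached to. Outcome (c) includes a procedure that the protocol places outside the excisional class and leaves out two that it places inside. A change in (c) can therefore come from LEEP, from cryotherapy, or from movement between them, and the planned analysis has no second row to tell these apart. Outcome (c) is also the plan's only measure of treatment, so nothing else in the analysis fills the gap.

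At stake is the statement the trial will make about excisions. A real reduction in LEEP could be diluted or hidden, and a reduction confined to cryotherapy could be read as success on the excisional objective.

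**Working it through.** **The plan's own figure.** Sample Size Estimates gives mean counts per eligible clinic of 560 women, 297 cytology specimens, 40 colposcopies and 4 LEEP or cryotherapy procedures. The stated treatment rate among women referred to colposcopy is 10%, and 4/40 = 10.0%, so it reproduces. As a share of all women, the denominator used in (c), the rate is 4/560 = 0.71%. The split between LEEP and cryotherapy is not given, nor is any count of conizations. An excisional rate therefore cannot be computed from the documents, and the rest is illustration over stated ranges.

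**How the pooled rate moves.** Let

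- s = LEEP share of the pooled count at baseline (assumed 0.5, 0.7, 0.9),
- r = relative fall in LEEP (assumed 50%),
- q = share of avoided LEEPs replaced by cryotherapy (0, 0.5, 1).

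With cryotherapy otherwise unchanged and one procedure per woman, the relative fall in the pooled rate is s × r × (1 − q).

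| s | q = 0 | q = 0.5 | q = 1 |
|---|---|---|---|
| 0.5 | 25% | 12.5% | 0% |
| 0.7 | 35% | 17.5% | 0% |
| 0.9 | 45% | 22.5% | 0% |

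In every cell LEEP has fallen by half.

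**The reverse case.** If cryotherapy halves and LEEP does not change, the pooled rate falls by (1 − s) × 0.5: 25%, 15% and 5% for s = 0.5, 0.7 and 0.9. Excisions have not changed.

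**Conization.** If conization were 0% to 20% of excisional procedures (a pure assumption), (c) would capture 100% to 80% of them. The documents do not narrow this range.

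**The numerators as written.** The illustrations above use LEEP or cryotherapy both before and after. The text adds colposcopy to the Post numerator only. Treating the mean counts as women, the numerator would go from 4 to between 40 (every treated woman also had colposcopy) and 44 (none did), a 10- to 11-fold rise with no change in practice. This must be corrected before any split of (c) can be read.

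**Precision.** With 3010 women per arm, 3010 × 4/560 = 21.5 pooled procedures are expected per arm over the period of the counts. If that period is one year (assumed), this is 21.5/4 = about 5 per quarter, and (c) is defined on quarters. Sample Size Estimates states that no power calculation was done for the LEEP outcome, so a split takes away no stated power.

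**The case against.** The strongest reply is that pooling fits another stated aim. The objectives open with overtreatment in general. Screening and Management Guidelines names LEEP and cryotherapy together as treatments that observation should replace in younger women. Choice of Comparators aims at less treatment of lesions likely to regress, whatever the method. For that aim, a woman moved from LEEP to cryotherapy is still treated, and no change in (c) is the right answer. This stands, and it is why the pooled rate should be kept.

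The Background also says that most practitioners prefer LEEP and that cryotherapy has become less popular. That makes the upper part of the assumed range for s more plausible and the pooled rate a better proxy. It does not remove the problem: at s = 0.9, full substitution still gives 0%, and a cryotherapy-only fall still gives 5%.

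Three stronger readings are tempting but lack support:

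- **That the patient tool steers women between methods.** The phrase "treatment options (cryotherapy vs. excisional therapy" is in Development of the PCA Intervention, but it belongs to the thematic areas for the focus groups. The listed themes of the intervention do not include that contrast, and the tool's content list mentions only which treatment procedures are available. A shift in method is possible; the documents do not predict one.
- **That pooling gives a wrong answer on preterm birth.** The Background does say "Two small meta-analysis found that excisional but not ablative treatment was associated with preterm birth", and it reports an association for cold-knife procedures. It also reports a raised risk after ablation against population comparators (OR 1.53, 1.32 to 1.78). Against untreated CIN, neither interval excludes 1 (excisional 1.25, 0.98 to 1.58; ablative 1.03, 0.9 to 1.18). The evidence on ablation is mixed, so the case for an excisional row rests on the stated objective.
- **That providers will move from LEEP to conization.** Nothing in the documents suggests that either intervention would cause this.

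Sparse data is a fair objection to expecting a firm answer from separate rows. It does not justify leaving the stated objective without a measure.

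**Conclusion.** The mismatch is in the text and does not depend on any assumption: the objective is excisional, while the outcome combines LEEP with an ablative method and names no conization. As defined, (c) cannot isolate a change in excisional procedures.

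A reader might go further and infer that (c) is invalid or cannot measure the objective at all. The documents do not support that, because (c) is a sound any-treatment measure once its numerators agree and a partial proxy for excisions where LEEP dominates.

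The size depends on a LEEP share that the documents do not give. Over assumed shares of 0.5 to 0.9, a halving of LEEP appears in (c) as a fall of anything from 45% down to 0%, depending on substitution. A halving of cryotherapy alone appears as a fall of 5% to 25%. The conization omission cannot be sized. The change is worth making because (c) is the only treatment outcome, although it is secondary and rests on few events.

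**What to change.** In Data Analyses, replace (c) with three rows, each a rate of women aged 21-29 over the same denominator:

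- **(c1) Excisional:** women with a claim for LEEP, laser conization or cold-knife conization. This is the measure of the stated objective.
- **(c2) Ablative:** women with a claim for cryotherapy, stating whether the other ablative methods named in the Background are included.
- **Any treatment:** women with (c1) or (c2), each counted once. This is the measure of overtreatment.

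List the claim codes for each row. Use the same numerator and code list in the Pre and Post periods and in all three groups, and remove colposcopy from the Post numerator. Amend the secondary-endpoint paragraph to match.

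The cost is a code list and two extra rows from claims the study already uses, provided those claims carry codes that separate the procedures; this should be confirmed first. The downside is imprecision: with about 4 pooled procedures per clinic, (c1) and (c2) should be reported as estimates with intervals beside the any-treatment row.
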